The balance program will consist of 12 exercises designed to challenge balance during stepping and walking. These exercises will include the activities listed in **Table 5**. Participants will complete up to 10 steps for each exercise and repeat the sequence of 12 exercises in two to three blocks up to a maximum of 30 minutes total. The number of steps to begin the program will be determined at baseline and progression will be tailored to the specific individual. A trainer will instruct the participant as to how to perform each of these exercises.

Table 5: Balance Training Program Exercises

Exercise	Repetitions (Maximum)
Side stepping to the left	10 steps
Side stepping to the right	10 steps
Backward stepping	10 steps
Forward stepping	10 steps
Alternating toe touch to box	5 touches per side
Tandem walking forward	10 steps
Tandem walking backward	10 steps
Walking on toes [1]	10 steps
Walking on heels [1]	10 steps
Walking with longer steps [1]	10 steps
Walking with shorter steps [1]	10 steps
Walking with wider steps [1]	10 steps

Progression of the balance exercise program will depend on the individual participant's ability to complete 3 sets of 10 repetitions of a particular exercise using smooth, controlled movements. At the weekly group session the trainer will determine if a participant should progress a particular exercise and will instruct the participant on how to progress. The participant will continue these exercises as instructed at home for the next week. Once a participant can complete 3 sets of a given exercise they will be given personalized instructions to progress the exercise. All participants will initially perform the exercises with hold support that will be progressed by instructing them to gradually reduce their reliance on external support. Once they can demonstrate that they can safely perform 3 sets of the exercise with minimal support the exercise will be progressed to be performed without support (**Table 6**). For the side and forward/backward stepping the participants will be instructed to take narrower steps and to vary the pace of the steps or to perform the exercise with their eyes closed. The side stepping exercises can also be made more challenging by using cross-over steps forward and backward in addition to direct lateral side steps. The alternating toe touches will be advanced by increasing the speed of the movements, varying the width of the base of support, and by instructing the participants to simultaneously move their arms by lifting light hand weights. The walking exercises will be progressed by varying step length, width, and speeds, stepping over objects, and using different lighting intensities.

Table 6: Balance Training Program Progression:

Exercise	Level A	Level B	Level C	Level D	Level E	Level F
Side stepping	10 steps Hold support	10 steps No support	10 steps Vary step length	10 steps Vary step speed	10 steps Eyes closed	
Forward/Backward stepping	10 steps Hold support	10 steps No support	10 steps Vary step length	10 steps Vary step speed	10 steps Cross-over steps	
Alternating toe touch to box	5 touches per side Hold support	5 touches per side No support	5 touches per side Increase speed	5 touches per side Vary width of base of support	5 touches per side Simultaneously move arms	5 touches per side Add hand weights
Tandem walking	10 steps Hold support	10 steps No support	10 steps Vary step speed	10 steps Vary light intensity		
Walking on toes/heels	10 steps Hold support	10 steps No support	10 steps Vary step length and width	10 steps Vary step speed	10 steps Vary light intensity	
Walking with varying step lengths and widths	10 steps Hold support	10 steps No support	10 steps Vary step speed	10 steps Step over objects	10 steps Vary light intensity	

The criterion for adequate compliance for a participant is to complete at least 75% of the balance training sessions. Several previously successful community and home based exercise programs were examined to determine what an expected level of compliance would be and how compliant a participant would need to be in order to observe an improvement in fall risk. One report of a multidimensional exercise program in community dwelling older adults showed that while performance on several balance scales improved significantly in both fully and partially (attended less than 75% of therapy sessions) adherent groups, the fully adherent group decreased their fall risk by 33% and the partially adherent group decreased their fall risk by 11% (89). Another study of a 12 week duration group-based exercise intervention that was found to significantly improve balance demonstrated a 78% attendance rate for group exercise sessions and 70% of the intervention participants attended at least three fourths of the sessions (90). In a study of diabetic patients there was a median exercise adherence of 87.5% over a 12 week training period (46). Interestingly, compared to these trials the "Feet First" trial of lower extremity exercise and walking on balance and fall incidence in diabetic neuropathy patients had only 45% protocol adherence in the intervention group and it was found that the degree of protocol adherence did not affect the trial results (48).

Participants will be given a balance exercise log to record the number of repetitions or steps completed of each exercise for each balance training session. Logs will be monitored and compliance assessed weekly. The goal is for participants to improve their balance and decrease their risk of falling. Balance and mobility will be assessed at base-line and 12 weeks.

Standard Care

The SC group will be assigned an interventionist assessor for the duration of the study. This assessor will meet with the subjects during their orientation meeting and will be provided information about falls and recommendations for fall prevention. There will be no directed program throughout the study. [Participants in the standard care group will also meet in person on a weekly basis for general education class regarding health and fall prevention but will not participate in an exercise class. They will also be asked to keep a log of any exercise that they perform at home. This will attempt to control for the effects of coming into a facility once a week in both the standard care and balance exercise intervention.]

At the completion of the study participants in the standard care group will receive instruction in the balance exercise program so that they may benefit from the program as well.

Intervention Timeline

Initially enrollment will be slow to pilot the intervention program and will aim to enroll one or two participants. The next two waves of patients will include 4 to 6 participants and afterwards each wave will include approximately 8 participants. This will require approximately 48 months to complete the intervention for 55 participants.

Table 7: Intervention Program Timeline:

Group (n)	Months																	
	1-3	4-6	7-9	10-12	13-15	16-18	10-21	22-24	25-27	28-30	31-33	34-36	37-39	40-42	43-45	46-48	49-51	52-54
1 (1 - 2)	x	x																
2 (4 - 6)			x	x														
3 (4 - 6)					x	x												
4 (8)							x	x										
5 (8)									x	x								
6 (8)											x	x						
7 (8)													x	x				
8 (8)														x	x			
Recruitment	x	x	x	x	x	x	x	x	x	x	x	x	x	x	x	x		
Screening	x	x	x	x	x	x	x	x	x	x	x	x	x	x	x	x	x	
Enrollment	x	x	x	x	x	x	x	x	x	x	x	x	x	x	x	x	x	
Outcome Assessment			x	x	x	x	x	x	x	x	x	x	x	x	x	x	x	x

Data management

The database manager utilizes a structured data entry system into a database with range checks on individual items and double keying to ensure accuracy. Data are entered into computers as per standard protocols. Data are cleaned and edited after being transported into a statistical software package. Protocols have been developed to handle missing or out of range values, documentation, file backup and archiving, and confidentiality procedures. The VA statistician, [name], will participate in the design of the protocols, choice of software platforms, computer data organization and structures, merging data sets, and data transport.

Blinding and Unblinding Plan

Only the research assistant and the biostatistician, neither of whom will be responsible for assessment of the outcome measures, will handle the randomization list with subjects' names. The treatment allocation list will be blinded to the investigators who measure the outcome measures. The main study data will be kept in a separate database with only the dummy ID. Unblinding prior to the completion of the study will be granted only for urgent clinical reasons, such as a subject has an urgent medical problem or has developed a serious adverse event, which requires the intervention allocation be made available. Otherwise, unblinding will occur on completion of all the recruitment and study measures. Unblinding is achieved by merging the main database with the treatment allocation list. At completion of the study, the study database will be locked. The statistician will finalize the statistical analysis plan and perform the analysis on the locked database.

The participants in the study will not be blinded to their group assignment since the intervention is an exercise intervention that requires active participation in both group and home exercise programs. However, the individuals performing the pre and post intervention assessments will be different individuals than those who lead the weekly group exercise sessions and are in regular contact with the participants. These assessors will be blinded to the participant's group assignment and will follow standardized protocols to perform and record the participants' performance on the outcome measures. To ensure that potential bias is minimized standardized instructions will be given to the participants and established protocols will be followed for measurement of the FSST (14) and DGI (15, 91). Assessment of the DGI on the GaitRite and the assessments performed on the ActiveStep are computerized measurements that will be automated.

Independent Data and Safety Monitoring Plan (DSMP)

The University of Maryland Institutional Review Board (UMIRB) and the Baltimore VA R&D committee will review the proposed level of risk and monitoring plan. All serious adverse events (SAEs) will be reported to the UMIRB and the VA R&D committee. The IRB will perform an annual review that may include any of the

following: adverse events (AEs), enrollment numbers, procedure reports, raw data, outcomes (primary, secondary), and preliminary analyses.

A data safety monitoring board (DSMB) will meet every six months or more frequently if a safety review is required. The DSMB will perform an unblinded review of adverse events, protocol deviations and changes, and enrollment numbers. Due to concerns regarding repeated testing for significance and given that this is a pilot study; interim analyses for efficacy will not be performed. Reasons for early termination of the trial will include an increased rate of serious adverse events related to the intervention or severe logistical or data quality problems that would make completion of the trial unfeasible.

Potential problems and limitations of the planned protocol

1) Choice of the FSST as the primary efficacy measure: The FSST was chosen as the primary efficacy measure because it has been shown to be a valid and sensitive measure for fall risk in populations of community dwelling older adults with excellent reliability and reproducibility. To our knowledge it has not been established what a clinically meaningful change in the FSST is for this population, but data from other groups of ambulatory patients with neurological disorders has been published (75) and we have powered the proposed study to examine for a smaller detectable mean change.

We considered comparing the proportion of participants with times on the FSST greater than 15 seconds (those at high risk for falls) in both groups at baseline and at 12 weeks, but the sample size required for this analysis was too large to accomplish within the constraints of the CDA-2. At baseline we would expect 30% of participants to be at risk for falls and we would hope to decrease this proportion by 40% in the balance exercise group. This would require a sample size of almost 400 subjects, which is not feasible for this pilot study.

2) We do not know how long of an intervention will be required to demonstrate an improvement in fall risk: It is possible that it can be seen after only a few weeks or it could take longer. The study was designed with a 12 week endpoint based on previously published data from studies of similar balance intervention programs. The FSST and DGI will be assessed at 4 and 8 weeks in addition to the primary endpoint at 12 weeks. This will be done to determine if the balance exercise intervention is effective as early as 4 weeks and if there is improvement over 12 weeks or if the intervention effect plateaus before 12 weeks. Alternatively if the 12 weeks of the balance exercise intervention is associated with an improvement in the FSST but it is not significant than a longer intervention may be required as part of a larger, more comprehensive study.

3) Choice of the balance exercise intervention: The intervention program chosen is a balance exercise program that can be easily taught and safely preformed by the study participants both at home and in a group setting. Previously published work has demonstrated the success of similar programs in reducing fall risk. A program that incorporates a targeted strengthening program as well might be more effective, but this is a potential area for future research.

4) Lack of a true control group: Due to the fact that participants enrolled in the proposed study are at risk for falls it is not ethical to provide them without standard care, which consists of education and guidance regarding falls. In addition at the end of the study those randomized to the control group will receive the same instruction in the balance exercise program as those randomized to the balance exercise group.

5) Effect of age on fall risk: Age and gender have been shown to be risk factors for falls. In this study randomization will not be stratified but these factors will be included as confounding variables in the final analyses. Stratifying by each of these variables would increase the required sample size. The objective of the currently proposed study is to demonstrate if a balance exercise program will improve fall risk in patients with the MetS and autonomic neuropathy. If successful, data obtained will be used to plan a larger study.

6) Participant compliance: We are experienced in providing long-term follow up in diet and physical activity interventions. Given the 12 weeks time period, the incentives provided, the proposed attrition rate, and the intrinsic value provided by the intervention that the proposed plan is feasible.

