The most common symptoms reported by subjects with neuropathy, “Do you have a dry mouth or dry eyes?” and “Are your feet colder than the rest of your body?” have similar frequencies in both men and women. **This data clearly indicates that there is a significance difference in the frequency and severity of autonomic symptoms between control and neuropathy subjects.** Furthermore, the SAS has power to distinguish between control subjects and those with peripheral neuropathy. The SAS symptom

Table 1. Association Between Nerve Conduction Studies or Intraepidermal Nerve Fiber Density and SAS

Item	SAS No. of Symptoms	SAS TIS
Sural SNAP	NS	NS (0.051)
Peroneal conduction velocity	NS	NS
Sum Score (Sural and Peroneal abnormalities)	NS	NS
IENFD	$P<0.0001$	$P<0.001$

NS = not significant

NS = not significant

score and TIS are not affected by age, gender, body mass index, weight, or height. This indicates that the SAS would perform well across subject groups in a clinical trial or epidemiological study and would be less likely to be affected by common confounding variables. Furthermore, there was a very strong association between the SAS and the intraepidermal nerve fiber density (IENFD), which is a sensitive and reliable measure of loss of small unmyelinated nerve fibers that includes sudomotor fibers (**Table 1**).

The neuropathy characteristically seen in patients with MetS is similar to that seen in IGT. Both are characteristically painful, predominantly small fiber neuropathies with autonomic involvement. Our preliminary work has shown that the SAS is a validated measure of autonomic symptoms in IGT. In the proposed study the SAS will be one of the tools used to detect the presence of symptoms of autonomic neuropathy in potential study participants. In addition one of the aims of the proposed study is to determine if the SAS can be used to detect the presence of increased fall risk in participants with MetS by determining if there is a correlation between the SAS symptom score and/or SAS TIS score and performance on the FSST.

RESEARCH DESIGN AND METHODS

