Sample Size Calculation

The FSST was chosen as the primary efficacy measure because it has been demonstrated to be a reliable and valid clinical test of fall risk. Importantly, it has been shown to have a higher sensitivity and specificity than the Timed Up and Go test, the Step Test and the Functional Reach Test for identifying differences between groups of older adults; non-fallers, non-multiple fallers, and multiple fallers (14). In normal controls the FSST has been shown to have a standard deviation of 2.34 seconds (74). A minimal detectable change has not been established in a population of elderly adults who are at risk for falls. However, in other populations of patients with neurological disorders that had a similar age and mean score at baseline the minimal detectable change estimate for the FSST was 4.6 seconds (75).

Table 3. Number of Subjects Required for a Range of Mean Differences in FSST

Smallest detectable mean difference in FSST (SD=2.34)	Number of subjects per group	Actual Power
1.0	87	0.800
1.5	40	0.808
2.0	23	0.809
3.0	11	0.816
4.0	7	0.835

Sample size per group required for to detect a specified mean difference in FSST at 12 weeks based on a two sample t test, power=0.8, significance level=0.05

Based on the FSST, the required sample size to detect a difference of 2.0 seconds is 23 participants per group. Based on results from similar intervention studies, the drop-out rate is up to 25% (14, 76). Allowing for a 10% drop-out rate in the standard care group, we will need to recruit 26 participants into the standard care group and 29 participants into the balance exercise group for a total of 55 participants.

Statistical Analyses

The two treatment groups will be compared using baseline demographic variables (age and gender) and relevant prognostic covariants (history of falls, BMI, abdominal circumference, fasting glucose, BP, lipids, SAS score, and baseline values of primary endpoints). These variables will be tested for baseline comparability using a univariate analysis. The variables will also be examined by stratified analysis to

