The network incorporates patient groups, local neurology and primary care practices, regional community and specialty hospitals, and VA clinics and hospitals that directly interact with neuromuscular clinics.

Advancing Science System (COMPASS) to recruit subjects for clinical research and establish a volunteer registry. COMPASS provides UM researchers with a search-and-discovery tool to identify potential study participants. These methods have been successful in current and previous trials the PI is conducting. In combination, we are confident that the recruitment goals can be met.

Measurements in subjects:

Measures of Fall Risk:

1) Four Square Step Test (FSST): The FSST involves the participant stepping over four canes that are laid on the ground at 90° angles to each other. A cross is formed on the floor by the four canes (90cm long) resting flat on the floor. The participant stands in one of the squares (square 1) formed by the canes facing forward. They are then instructed to step as quickly as possible into each square in a specified sequence; rotating clockwise around the “plus sign” by moving forward to the right, backward, and to the left. They then reverse their direction and move in a counterclockwise direction (14). The score is recorded as the time taken to complete the sequence. Two FSSTs are completed and the best time is taken as the score.

A cutoff score of greater than 15 seconds on the FSST has been identified to categorize subjects as multiple fallers. This cutoff score has a positive predictive value of 86% and a negative predictive value of 94% in a population of community dwelling older adults. The FSST was found to have a higher combined sensitivity and specificity than the Timed Up and Go test, Step Test, and Functional Reach Test in this patient population (14).

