2) Dynamic Gait Index (DGI): [An instrumented DGI will be performed and gait variables of time in single or double support as well as step length and width and gait velocity will be measured.] The clinical DGI will also be performed. The DGI is a measure of functional balance during walking and its score has been shown to be responsive to change after interventions in older adults with impaired balance. However, the DGI score has not been found to be predictive of falls in two studies of community dwelling older adults (15, 81). The DGI had a lower sensitivity (59%) than the FSST when used to identify fallers vs. non-fallers in community dwelling adults over age 65 years (15). To our knowledge the sensitivity of the DGI and the FSST to detect a change in function has not been compared. However, the FSST has been found to have a good correlation with the DGI in people with vestibular disorders and ambulant people with multiple sclerosis (75, 82). In terms of the ability of the DGI to detect change, a 2012 study of community dwelling older adults found that the DGI had poor responsiveness (ES=0.27) after a 16 week exercise trial (18).

As a novel and more quantitative measurement we propose performing the level walking items of the DGI on an instrumented gait mat (GaitRite). This would allow for examination of the temporal and spatial characteristics of gait during performance of the DGI and the findings could potentially be used to provide novel insights on individual items, [such as time in single or double support as well as step length and width and gait velocity,] that potentially may be more revealing in identifying balance and gait deficits than just a timed performance score. The rating criterion for the DGI involves observational quantification of functional gait performance and deviations may be missed. However, the gait mat performs this analysis in an objective, detailed, and reproducible manner.

3) ActiveStep: The ActiveStep treadmill system is another sophisticated tool that is used to assess balance performance and fall risk. [Specifically we will examine the presence of recovery steps after a balance challenge.] This assessment tool is different than the FSST and DGI in that it quantifies reactive balance control. Rapid changes in the movement of the treadmill belt, either from rest or during ongoing gait, produce large postural disturbances that require rapid compensatory responses in order to maintain balance and prevent a fall.

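### The aim of showing that the SAS can detect increased fall risk rests only on whether it correlates with the FSST, which shows association and not detection

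*Combined protocol and SAP*

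**What the plan says.** The aim appears in the protocol's Preliminary Studies, in the closing paragraph of the section on autonomic abnormalities in subjects with IGR neuropathy. It puts a question about detection and answers it with a correlation; the SAS is meant to "detect the presence of increased fall risk in participants with MetS by determining if there is a correlation between the SAS symptom score". The sentence then lets the total impact score count as well or instead, in these words: "and/or SAS TIS score and performance on the FSST". No test, significance level, minimum correlation or SAS cut-off for fall risk is given.

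The aim is not taken up later. The hypotheses under Statistical Analyses and Table 4 do not include it, and that section uses the SAS score only as a baseline covariate.

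The protocol does contain what an accuracy analysis would need:

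- Measures of Fall Risk gives a high-risk definition: "A cutoff score of greater than 15 seconds on the FSST has been identified to categorize subjects as multiple fallers".
- Item 1 of the potential problems and limitations gives an expected share: "At baseline we would expect 30% of participants to be at risk for falls". The same item ties being at risk to an FSST above 15 seconds.
- Table 2 schedules the SAS at screening and the FSST at enrollment, so both are available before the intervention starts.
- The other fall-risk tools are described by accuracy: 84% sensitivity and 88% specificity for the ABC scale (Outcome Measures), and 85% sensitivity with 86% positive predictive value for the FSST (Measures of Fall Risk).

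**The concern.** The question is about detection, while the method answers a question about association. Detection asks how well the SAS separates participants above 15 seconds from the rest, and how many it would misclassify at a usable cut-off. A correlation test asks only whether the relation differs from zero. A weak relation can pass that test in a sample of 55 while the two groups still overlap heavily. Allowing either of two SAS scores to count makes a positive finding easier still.

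The Objectives describe MetS patients with early neuropathy and high fall risk as the group to target with interventions, and the Background says the pilot will inform a later trial. A statement that the SAS detects fall risk, resting on a significant correlation alone, would claim more than the analysis can show.

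**Working it through.** **Inputs from the protocol.** Sample Size Calculation: "29 participants into the balance exercise group for a total of 55 participants" (26 + 29 = 55). High risk is an FSST above 15 seconds. The expected share is 30%, so 0.30 × 55 = 16.5, taken as 16 high-risk and 39 others.

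**Assumptions, because the protocol gives no figure.** A two-sided test at 0.05 for the SAS aim; bivariate normal SAS and FSST; a true correlation r of 0.2 to 0.4; a correlation of 0.8 between the two SAS scores (0.5 to 0.9 as a range); all 55 with baseline data.

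**The plan's own figures.** There is none for the SAS aim. Table 3 is "based on a two sample t test, power=0.8, significance level=0.05". With SD 2.34 and a difference of 2.0 seconds, a two-sided t test with 23 per group has power 0.809, as printed. For the 15-second cut-off, item 1 of the limitations wants the 30% lowered by 40%, that is to 18%. Comparing 0.30 with 0.18 needs 198 per arm, 396 in all, which agrees with the protocol's figure of nearly 400.

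**Step 1: the smallest significant correlation.** Critical r = t / √(n − 2 + t²), with t = 2.006 on 53 degrees of freedom: 2.006 / √(53 + 4.023) = 0.266. That is r² = 0.07, or 7% shared variance.

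**Step 2: how often one score passes.** Fisher approximation: power = Φ(atanh(r) × √52 − 1.96).
- r = 0.3: Φ(0.3095 × 7.211 − 1.96) = Φ(0.272) = 0.61; simulation gives 0.62.
- r = 0.4: Φ(0.4236 × 7.211 − 1.96) = Φ(1.095) = 0.86; simulation gives 0.87.

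**Step 3: discrimination and passing rate side by side** (high risk = the top 30% of FSST; passing rates by simulation).

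| True r | AUC | One score significant | Either score (correlated 0.8) |
|---|---|---|---|
| 0.2 | 0.59 | 31% | 41% |
| 0.3 | 0.64 | 62% | 72% |
| 0.4 | 0.69 | 87% | 92% |

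If the two SAS scores correlate anywhere from 0.5 to 0.9, the last column becomes 38–47%, 69–79% and 91–96%. With no true correlation, the either-score rule is positive 7–9% of the time.

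**Step 4: what the errors look like depends on the cut-off.** Sensitivity / specificity for an FSST above 15 seconds:

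| Share flagged by SAS | r = 0.3 | r = 0.4 |
|---|---|---|
| 30% | 43% / 75% | 47% / 77% |
| 50% | 64% / 56% | 69% / 58% |
| 80% | 89% / 24% | 92% / 25% |

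A lower cut-off exchanges missed cases for false alarms. The AUC is the same in every row.

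**Step 5: precision of the AUC.** Hanley–McNeil standard error with 16 versus 39: 0.085 at AUC 0.66 and 0.078 at AUC 0.75. Half-widths: 1.96 × 0.0846 = 0.166 and 1.96 × 0.0781 = 0.153.

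**Step 6: would an AUC interval excluding 0.5 be enough?** In simulation under the same model, that rule still passes about 39% of the time at r = 0.3 and 63% at r = 0.4. It too tests only for some association.

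**The case against.** The strongest reply is that no formal decision rule exists. One sentence in a background section speaks of a correlation, with no test, alpha or consequence attached, and the randomised comparison does not depend on it. This stands: the 0.05 test is an assumption, and it limits the severity. It does not remove the mismatch, because correlation is the only method offered for a detection question and no later section adds another.

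A reader might go further in three ways that the documents do not support.

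- **That the SAS would miss most high-risk participants.** This depends on a cut-off that the plan does not set for fall risk. The only SAS cut-off given (more than 3 symptoms or an impact score above 7) is an entry criterion. The pilot medians were 5 in fallers and 3.5 in non-fallers for symptoms, and 14 and 9 for impact. All lie above it, so it would probably flag most participants. Poor specificity is then the likelier failure.
- **That the error rate is many times the nominal 5%.** The 5% applies when the true correlation is zero. The percentages in Step 3 are power at non-zero correlations.
- **That the SAS should be measured against the DGI figure** ("The DGI had a lower sensitivity (59%) than the FSST when used to identify fallers vs. non-fallers"). That figure concerns fallers versus non-fallers in adults over 65 and is given without a specificity. Here the reference would be another test, the FSST.

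Two further objections also stand. The SAS is one of two routes into the trial, so its values in the sample are selected, which the calculations do not model. An AUC analysis shares that limit, and Step 6 shows that it needs a stated threshold to be any better than the correlation.

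**Conclusion.** The concern holds as a mismatch between aim and method. Evidence of a correlation between the SAS and the FSST would not show that the SAS detects increased fall risk, and the plan contains no analysis that would. Under the stated assumptions, a scale with an AUC of 0.64 to 0.69 would show a significant correlation in about 62% to 87% of trials, or 72% to 92% if either score counts. These figures depend on bivariate normality, the assumed two-sided 0.05 test, the full 55 at baseline, and no allowance for selection on the SAS. Whether the weakness would show as low sensitivity or low specificity cannot be settled from the documents. The severity is minor: the aim is not primary, and neither the FSST comparison nor its sample size is affected.

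**What to change.** Amend the statement of the SAS aim and list it with the hypotheses under Statistical Analyses, as follows.

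1. Name one SAS score as the main one for this aim; the other is supportive.
2. Report its baseline correlation with the FSST and a 95% confidence interval, as a measure of association only.
3. Add the AUC for an FSST above 15 seconds with a 95% confidence interval, and sensitivity and specificity across SAS cut-offs, all as estimates.
4. State that neither a significant correlation nor an AUC interval that merely excludes 0.5 will be reported as showing that the SAS can detect fall risk. A detection statement needs the lower confidence limit to exceed a useful AUC fixed in advance. Otherwise the result is described as association and hypothesis-generating.
5. State the limits: about 16 of 55 participants expected above 15 seconds, giving an AUC half-width of about 0.15 to 0.17; SAS values selected by the entry criteria; and a 15-second cut-off whose accuracy was reported in adults over 65, while this trial enrols ages 50 to 70.

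The cost is some wording and one extra analysis of data already scheduled. The downside is that a detection claim becomes harder to make, and with this sample it may well not be reached.
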